### Concomitant medications/products and concomitant administration

At each participant contact over the phone or in-person, the investigator should question the participant about any medication/product taken and injection received by the participant.

### Recording of prior and concomitant medications/products and concomitant administration

The following prior and concomitant medications/products/vaccines must be recorded in the eCRF if administered during the indicated recording period:

- All concomitant medications/products, except vitamins and dietary supplements, administered from 14 days prior to screening up to 28 days following any dose of study product.
- Any concomitant vaccination administered in the period starting from screening up to study end.
- Prophylactic medication (*i.e.* medication administered in the absence of ANY symptom and in anticipation of a reaction to the injection). *E.g.* an anti-pyretic is considered to be prophylactic when it is given in the absence of fever and any other symptom, to prevent fever from occurring.
- Any concomitant medication/product/vaccine relevant to a SAE\* or administered at any time during the study period for the treatment of a SAE\*, or administered at any time during the study for treatment of an adverse event leading to study termination, or treatment of an adverse event requiring a medically attended visit.

*\*SAEs that are required to be reported per protocol.*

### **Concomitant medications/products/vaccines that may lead to the elimination of a participant from according-to-protocol (ATP) analyses**

The use of the following concomitant medications/products/vaccines will not require withdrawal of the participant from the study but may determine a participant's evaluability in the according-to-protocol (ATP) analysis:

- Any investigational or non-registered product (drug or vaccine) other than the study product(s) used during the study period.
- A vaccine not foreseen by the study protocol administered during the period starting from 14 days before injection and ending 14 days after a study vaccine injection. It should be noted that in case an emergency mass vaccination for a unforeseen public health threat other than COVID-19 is organized by the public health authorities, outside the routine immunization program, the time period described above can be reduced if necessary for that vaccine provided it is authorized by the regulatory authority and used according to its package insert and according to the local governmental recommendations and provided a written approval of the Sponsor is obtained.
- Immunosuppressants or other immune-modifying drugs administered chronically (*i.e.* more than 14 days) during the study period (for corticosteroids, this will mean prednisone  $\geq 20$  mg/day, or equivalent). Inhaled and topical steroids are allowed.
- Long-acting immune-modifying drug administered at any time during the study period (*e.g.* infliximab).

- Immunoglobulins and/or any blood products administered during the study period.

### **Intercurrent medical conditions that may lead to elimination of a participant from ATP analyses**

At each participant contact subsequent to the First Injection Visit, it must be verified if the participant has experienced or is experiencing any intercurrent medical condition. If it is the case, the condition(s) must be recorded in the eCRF.

Participants may be eliminated from the ATP cohort for immunogenicity if, during the study, they incur a condition that has the capability of altering their immune response (e.g. confirmed influenza infection) or if they become diagnosed with an immunological disorder.

## **7. SAFETY**

A primary objective of this study focuses on the tolerability and safety of receiving two doses of  $5 \times 10^{10}$ vp Ad5-nCoV vaccine. This will be measured by the incidence of SAE and MAE within 52 weeks of receiving the vaccine and solicited AE (*local* injection site reactions and *general* reactions within the seven days following vaccination) and unsolicited AE within 28 days after vaccination.

The investigator or site staff is/are responsible for the detection, documentation and reporting of events meeting the criteria and definition of an AE, MAE, or SAE as provided in this protocol. Each participant will be instructed to contact the investigator immediately should they manifest any signs or symptoms they perceive as serious.

Table 3. Adverse Event Reporting:

Participants	30 min observation	First Injection Visit- Day 7	Day 8-28	Beyond day 29 until week 52
All	Post injection AE or SAE only	Solicited AEs and unsolicited AEs SAE and MAE	Any unsolicited AE only SAE and MAE	SAE and MAE only

### **7.1 Definitions of an adverse event**

An AE is “an untoward medical occurrence in a clinical investigation subject, temporally associated with the use of a medicinal product, whether or not considered related to the medicinal product.” A medical attended AE (MAE) is an AE that requires a visit with the healthcare system. A serious AE (SAE) is an untoward medical occurrence that results in death, is life-threatening (that is, there was a risk of death at the time of the event), requires

hospitalization or prolongation of existing hospitalization occurs, results in disability/incapacity, or is a congenital anomaly/birth defect in the offspring of a study subject.

An AE can therefore be any unfavourable and unintended sign (including an abnormal laboratory finding), symptom, or disease (new or exacerbated) temporally associated with the use of a medicinal product.

Examples of an AE include:

- Significant or unexpected worsening or exacerbation of the condition/indication under study.
- Exacerbation of a chronic or intermittent pre-existing condition including either an increase in frequency and/or intensity of the condition.
- New conditions detected or diagnosed after investigational product administration even though they may have been present prior to the start of the study.
- Signs, symptoms, or the clinical sequelae of a suspected interaction.
- Signs, symptoms, or the clinical sequelae of a suspected overdose of either investigational product or a concurrent medication (overdose *per se* should not be reported as an AE/SAE).
- Signs, symptoms temporally associated with product administration.
- Significant failure of expected pharmacological or biological action.
- Pre- or post-treatment events that occur as a result of protocol-mandated procedures (i.e. invasive procedures, modification of participant's previous therapeutic regimen).

AEs to be recorded as endpoints (solicited AEs) are described below.

All other AEs will be recorded as unsolicited AEs.

Examples of an AE DO NOT include:

- Medical or surgical procedures (e.g. endoscopy, appendectomy); the condition that leads to the procedure is an AE/SAE.
- Situations where an untoward medical occurrence did not occur (e.g. social and/or convenience admission to a hospital, admission for routine examination).
- Anticipated day-to-day fluctuations of pre-existing disease(s) or condition(s) present or detected at the start of the study that do not worsen.
- Pre-existing conditions or signs and/or symptoms present in a participant prior to the first study injection. These events will be recorded in the medical history.

### **Solicited adverse events**

A **solicited adverse event** (AE) is a pre-specified outcome that the participant is asked to record as present or not, and if present, to apply an intensity rating. Solicited AE are collected daily from Days 0 to 7 following administration of the study vaccine. An **unsolicited** event is one that

the participant identifies when asked in a non-leading manner if there have been any changes in their health since the last participant contact.

Solicited AEs (Solicited local (injection-site) and general AEs) occurring during the 7-day participant contact period after injection will be recorded.

### **Solicited local (injection-site) adverse events**

The following local (injection-site) AEs will be solicited:

- Pain at injection site
- Redness at injection site
- Swelling at injection site

### **Solicited general adverse events**

The following general AEs will be solicited:

- Drowsiness
- Fever
- Headache
- Nausea
- Diarrhea
- Vomiting
- Generalized muscle aches

*Note: Temperature will be recorded in the evening. Should additional temperature measurements be performed at other times of day, the highest temperature will be recorded in the eCRF.*

### **Definition of a serious adverse event**

An SAE is any untoward medical occurrence that:

- a. Results in death,
- b. Is life-threatening,

*Note: The term ‘life-threatening’ in the definition of ‘serious’ refers to an event in which the participant was at risk of death at the time of the event. It does not refer to an event, which hypothetically might have caused death, had it been more severe.*

- c. Requires hospitalisation or prolongation of existing hospitalisation,

*Note: In general, hospitalisation signifies that the participant has been admitted at the hospital or emergency ward for observation and/or treatment that would not have been appropriate in the physician’s office or in an out-patient setting. Complications that occur during*

hospitalisation are also considered AEs. If a complication prolongs hospitalisation or fulfils any other serious criteria, the event will also be considered serious. When in doubt as to whether 'hospitalisation' occurred or was necessary, the AE should be considered serious.

Hospitalisation for elective treatment of a pre-existing condition (known or diagnosed prior to informed consent signature) that did not worsen from baseline is NOT considered an AE.

d. Results in disability/incapacity,

Note: The term disability means a substantial disruption of a person's ability to conduct normal life functions. This definition is not intended to include experiences of relatively minor medical significance such as uncomplicated headache, nausea, vomiting, diarrhoea, influenza like illness, and accidental trauma (e.g. sprained ankle) which may interfere or prevent everyday life functions but do not constitute a substantial disruption.

e. Congenital anomaly/birth defects,

Note: Medical judgment should be exercised in deciding whether reporting is appropriate in other situations, such as important medical events that may not be immediately life-threatening or result in death or hospitalisation but may jeopardise the participant or may require medical or surgical intervention to prevent one of the other outcomes listed in the above definition. These should also be considered serious. Examples of such events are invasive or malignant cancers, intensive treatment in an emergency room or at home for allergic bronchospasm, congenital anomaly/birth defects, blood dyscrasias, or convulsions that do not result in hospitalisation.

**Clinical laboratory parameters and other abnormal assessments qualifying as adverse events or serious adverse events**

Although routine clinical laboratory monitoring is not a part of this phase IIb trial, a participant may undergo laboratory testing for other reasons as part of their normal medical care. In absence of diagnosis, abnormal laboratory findings (e.g. clinical chemistry, haematology,) or other abnormal assessments (e.g. physical examination findings) that are judged by the investigator to be clinically significant will be recorded as AE or SAE if they meet the definition of an AE or SAE. Stable and or chronic health conditions that were present at baseline and significantly worsen following the start of the study will also be reported as AEs or SAEs. However, abnormal laboratory findings associated with existing health condition, unless judged by the investigator as more severe than expected for the participant's condition, will not be reported as AEs or SAEs. The investigator will exercise his or her medical and scientific judgment in deciding whether an abnormal laboratory finding, or other abnormal assessment is clinically significant.

**7.2 Detection of adverse events**

All participants will be instructed on the recognition of symptoms and signs by the study staff. Monitoring for any signs or symptoms of COVID-19 is instrumental in evaluating the efficacy of

the candidate vaccine. Participants will be monitored for incidence of local and systemic AE, in addition to monitoring for SAE. These participants will be instructed on how to take their temperature orally, as well as to record any symptoms in their e-diary or diary card for 28 days after receiving the vaccination. A thermometer and access to an e-diary or a paper diary card will be provided to record solicited AEs from First Injection Visit-Day 7, and unsolicited AEs from First Injection Visit-Day 28. Participants will review their completed e-diary or diary card with study staff at their second in-person visit on Day 28. A second e-diary or a paper diary card will be provided at Day 56 and will be collected at Day 84. Data collected from e-diaries and diary cards will be uploaded into the participant's eCRF. All participants will be monitored for the incidence of SAE and MAE up to 52 weeks after receiving the vaccination, via a phone call every 4 weeks. Participants will be instructed to contact study staff by phone (24 hours a day), if a MAE or SAE occurs.

AE Type	Solicited AEs/ Unsolicited AEs/MAEs/SAEs
Method of 'solicited' participant contact	E-diary or diary card
Method of 'unsolicited' participant contact	E-diary or diary card**
Method for reporting SAEs/MAEs	SAE report forms
Method for reporting pregnancies	Pregnancy report forms

#### Time period for detecting and recording adverse events and serious adverse events

All AEs starting within 28 days following administration of the dose of the study product must be recorded into the appropriate section of the eCRF, irrespective of intensity or whether or not they are considered injection related.

The time period for collecting and recording SAEs and MAEs in all participants will begin at the first receipt of study product/comparator and will end on Day 364.

All AEs/SAEs leading to withdrawal from the study will be collected and recorded from the time of the first receipt of study product. SAEs that are related to the investigational product will be collected and recorded from the time of the first receipt of study product/comparator until the participant is discharged from the study.

In addition to the above-mentioned reporting requirements and in order to fulfill international reporting obligations, SAEs that are related to study participation (i.e. protocol-mandated procedures, invasive tests, a change from existing therapy) will be collected and recorded from the time the participant consents to participate in the study until she/he is discharged from the study.

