In its original version, the protocol limited inclusion to "people living with HIV on stable treatment and virologically suppressed..." .

Likewise, the design was double-blind versus placebo in a 2:1 ratio.

The advancement of the national vaccination reduced the possibilities of access to the study under such design, for which this protocol amendment was proposed.

Volunteers initially included in the study will receive two doses of the vaccine and will continue their follow-up as established in the protocol.

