#### 3.2 Study Groups

A total of 500 participants will be enrolled to receive the vaccine. All participants will be monitored for solicited adverse events for 7 days, unsolicited adverse events for 28 days, SAEs and MAEs for the one year duration of the study, and antibody measurements at baseline, Day 28, Day 84, week 24, and week 52. A subset of 50 participants will have cellular immunity measured at those same intervals.

This protocol amendment provides for unblinding of participants who were entered into the study in the double-blind schedule. For participants who entered the double-blind schedule, the visit process will be as follows:

a) Sites will receive an unblinding list detailing participants who received placebo or study vaccine. Participants who received placebo will be invited to continue in the study under the

open-label study scheme and should make visits from V1.B (first vaccine) onwards, after signing the informed consent, completing visits on day 28 (V2.B), day 56 (second dose) (V3.B), day 84 (V4.B), week 24 (V5.B) and week 52 (V6.B). In this group of participants already enrolled, no antibody dosage collection will be performed at the V1B visit; the V1 values at study entry will be taken. The letter B is added to the visits to differentiate this group of participants who must reorganize the schedule of visits from the administration of the first dose of CoVID vaccine after the unblinding. The procedures for this group are detailed in Table 2.

b) Participants who, after the unblinding, are found to have received study vaccine at the initial visit, will complete the visits established by protocol together with the administration of dose 2 of the study (day 56) onwards, after signing the informed consent. In this group of participants there will be no changes in the nomenclature of the visits.

For both arms (placebo and study vaccine), efficacy contacts are restarted with the second injection visit.

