### 9.2 Study Population and Analysis Sets

#### 9.2.1 Study Population

##### Intent-to-Treat Cohort

The intent-to-treat cohort consists of all participants who receive at least one study injection, regardless of their protocol adherence and continued participation in the study. Participants will be analyzed according to their randomized treatment. Participants who withdraw from the study will be included up to the date of their study withdrawal.

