### **9.3.3 Safety Analysis**

#### **Primary Safety Endpoint:**

- The incidence of solicited adverse reactions within 7 days after vaccination.
- The incidence of unsolicited adverse events within 28 days after vaccination.
- The incidence of detectable viral load 24 and 52 weeks after vaccination
- The incidence of serious adverse events (SAE) and medically attended adverse events (MAE) within 52 weeks after vaccination in all participants.

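### The SAE/MAE clock and the intent-to-treat set keep blinded-design wording, so nothing keeps placebo-period events and placebo-only people out of a primary safety rate

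*Protocol*

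**What the plan says.** Section 7.2, in the part on time periods, says that SAE and MAE recording in all participants "will begin at the first receipt of study product/comparator and will end on Day 364". Earlier in the same section: "All participants will be monitored for the incidence of SAE and MAE up to 52 weeks after receiving the vaccination".

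Section 9.3.3 lists as a primary safety endpoint: "The incidence of serious adverse events (SAE) and medically attended adverse events (MAE) within 52 weeks after vaccination in all participants".

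Section 1.3 describes the design before the amendment: "Likewise, the design was double-blind versus placebo in a 2:1 ratio". Under the amendment everyone is to receive Ad5-nCoV. Section 3.2 invites former placebo recipients to continue, and says that they "should make visits from V1.B (first vaccine) onwards, after signing the informed consent". Their B visits run to week 52 (V6.B), and Table 2 labels V1.B as Day 0.

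Section 9.2.1: "The intent-to-treat cohort consists of all participants who receive at least one study injection". It adds that participants are analysed by the arm to which they were randomised, and that those who withdraw count up to withdrawal. Section 9.3.3 runs the safety analysis in this cohort and in the per-protocol cohort.

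**The concern.** The endpoint is counted from vaccination, while the recording rule is counted from the first injection of either kind. For most participants these are the same day. For people first given placebo they are not, and section 7.2 does not say which day is their Day 0.

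The analysis set does not resolve this. A placebo injection given under the blinded protocol is naturally read as a study injection, so someone who had placebo and declined the open-label phase would stay in the denominator of a vaccine safety rate. Someone who crossed over would, under the randomised-arm rule, carry post-vaccine events in the placebo column. Participants enrolled after the amendment have no randomised arm, so the rule cannot be applied to them at all.

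At stake is a primary safety rate in a trial that section 1.3 says is run to collect safety data in people with HIV.

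**Working it through.** **Inputs**

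- Recording period: first product or comparator injection to Day 364 (section 7.2).
- Endpoint window: 52 weeks after vaccination (section 9.3.3).
- Day 364 is the week 52 visit (section 3.5).
- Former placebo group: Day 0 is V1.B, the end is week 52 at V6.B, with safety contacts every 4 weeks (section 3.2, Table 2).
- Study conclusion: 52 weeks after vaccination (section 5.2).
- Blinded allocation 2:1 (section 1.3); 500 participants to be enrolled (section 3.2).
- Not given: the days X from placebo to V1.B, and the number M enrolled under blinding.

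**Step 1. Reproduce the plan's figure.** 52 × 7 = 364 days. Day 364 and the 52-week endpoint agree when Day 0 is the first vaccine dose.

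**Step 2. Apply the rule to a former placebo recipient.** Recording starts X days before vaccine. The end depends on which Day 0 is used.

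- Day 0 = V1.B: time after vaccine = 364 days = 52 weeks for any X. Total recorded = 364 + X days.
- Day 0 = placebo injection: time after vaccine = 364 − X days.

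With X assumed to be 56 or 168 days:

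| X (assumed) | Weeks recorded before vaccine | Weeks after vaccine, Day 0 = V1.B | Weeks after vaccine, Day 0 = placebo |
|---|---|---|---|
| 56 days | 8 | 52 | (364 − 56)/7 = 44 |
| 168 days | 24 | 52 | (364 − 168)/7 = 28 |

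The weeks before vaccine are recorded on either reading. The loss after vaccine appears only in the last column.

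**Step 3. Follow those weeks into the analysis.** The endpoint wording, applied literally, would leave them out. No rule in sections 7.2, 9.2.1 or 9.3.3 says so or states how such events are classified. If they are counted, the participant has 52 + X/7 weeks at risk against 52 for others, which tends to raise a per-person incidence. Adding placebo-only people to the denominator tends to lower it if the vaccine causes events. The net direction is not fixed.

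**Step 4. Assign arms under section 9.2.1.** A participant randomised to placebo who then receives Ad5-nCoV at V1.B is analysed as placebo throughout, including the 52 weeks after vaccine. Section 9.3.3 still plans Fisher's exact test of adverse event rates between treatment and control, so those events would fall on the control side.

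**Step 5. Number affected.** At 2:1, M/3 people had placebo. For orientation only, assume that M is 60 or 300, that the 500 include them, that all cross over, and that all complete follow-up. Then 20 or 100 people are affected: 20/500 = 4% or 100/500 = 20%. With Day 0 = V1.B, the share of all recorded person-time that precedes vaccine is (M/3)X / (500 × 364 + (M/3)X):

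- M = 60, X = 56: 1,120/183,120 = 0.6%.
- M = 300, X = 168: 16,800/198,800 = 8.5%.

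These values of M and X are assumptions, not estimates.

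**The case against.** A reader might infer that section 7.2 cuts former placebo recipients' follow-up to less than 52 weeks after vaccine. The documents do not support that. It requires counting Day 364 from the placebo injection, and no section says to do so. Section 3.2 and Table 2 reset this group's Day 0 to V1.B and follow it to V6.B, section 5.2 ends the study 52 weeks after vaccination, and the opening of section 7.2 monitors everyone for that long. Section 7.2 also records product-related SAEs until discharge. The risk is limited to a site that reads the Day 364 sentence on its own.

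A second inference is that recording from the placebo injection is itself wrong. It is not: safety events in the blinded period have to be captured. Collection is separate from the endpoint, and nothing states that placebo-period events count as post-vaccination.

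It can also be said that the per-protocol cohort, which requires the right treatment and number of doses, would drop placebo-only people, and that the intent-to-treat definition does not say whether placebo counts as a study injection. Both are fair, but the intent-to-treat analysis is also planned for safety, and its text does not exclude these people. Section 9.2.1 leaves details of the per-protocol set to the SAP, whereas it fixes the intent-to-treat set and the randomised-arm rule itself.

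What stands is an unstated Day 0, the lack of a rule separating placebo-period events from the endpoint, and a cohort definition that does not fit the open-label trial.

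**Conclusion.** The point holds as a failure to reconcile section 7.2 (time periods) and section 9.2.1 with sections 3.2, 3.4 (Table 2), the opening of 7.2, and 9.3.3. It should be corrected because it touches a primary safety endpoint. It does not show lost follow-up after vaccine.

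It concerns only people first given placebo, about one third of those enrolled under blinding. The effect on the SAE and MAE rates cannot be given in size or direction, because neither the number enrolled under blinding nor the interval from placebo to V1.B is stated. The conclusion assumes that a placebo injection counts as a study injection and that the randomised-arm rule is applied literally. A SAP could reclassify recorded events, but it would then depart from the definition that the protocol fixes.

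**What to change.** - **Section 7.2:** keep SAE and MAE collection from the first injection of any kind. Moving its start to V1.B would lose the placebo-period events. Add that, for the primary endpoint, Day 0 is the first Ad5-nCoV dose (V1, or V1.B for former placebo recipients) and the window ends 364 days later (Week 52, or V6.B). This brings the sentence into line with sections 3.2, 3.4 (Table 2) and 9.3.3 and with the opening of 7.2.
- **Reporting:** list events between the placebo injection and V1.B separately, outside the endpoint.
- **Section 9.2.1:** define the safety set as participants with at least one dose of Ad5-nCoV, analysed by the vaccine actually received, and name that set in section 9.3.3.

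The cost is wording only. V6.B and the four-weekly safety contacts are already planned, so no visit, sample or participant is added.
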